The present non-interventional study will aim to provide a Europe-wide picture of (i) the demographic and clinical features of HFrEF patients managed in the outpatient sector and the diagnostic and pharmacologic intervention they receive; (ii) the demographic and clinical features of patients the treating physician decided to start sacubitril/valsartan, the pattern of administration of this drug, the diagnostic and therapeutic intervention these patients receive and the safety and tolerability profile of this drug in real life.

Main objectives:

- To describe the profile of patients initiated on sacubitril/valsartan and patients continued on SoC in the outpatient sector in terms of demographics, medical history, HF status, comorbidity burden
- To describe the profile of sacubitril/valsartan patients not reaching and maintaining the target dose of 200 mg twice daily in terms of demographics, medical history, HF status, comorbidity burden as compared with patients reaching the target dose

Additional objectives:

- To describe the overall HFrEF population managed in the outpatient sector in Europe in terms of demographics, medical history, comorbidity burden and previous cardiovascular (CV) events rate
- To describe HF-treatment (pharmacological and non-pharmacological) in the outpatient sector in Europe and in individual countries/country clusters
- To describe the starting dose, titration and maintenance dose of sacubitril/valsartan in patients with different anamnestic and demographic characteristics
- To assess the rates of major HF related outcomes (death, hospitalizations, major CV events)
- To describe Healthcare Resource Utilization in HFrEF patients managed in the European routine practice
- To describe safety and tolerability features of sacubitril/valsartan in real-world HF patients
- To describe the quality of life (QoL) during follow-up (only in those sites where the EQ-5D and/or KCCQ QoL questionnaires are part of routine CHF management)
- To describe the levels of BNP / NT-proBNP (only if these measurements are available or at sites where these measurements are performed within the routine CHF management)

7 Research methods

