7.2 Setting

7.2.1 Population

The present study will include consecutive HFrEF patients treated by office-based cardiologists or selected primary care physicians (recognized as HF specialists) across Europe.

The study will include overall 6000 patients on SoC and 6000 patients on sacubitril/valsartan.

Considering that the different local regulations on patient management and reimbursement can significantly impact clinical practice, patient numbers will be allocated to bigger countries and/or clusters of smaller countries with similar healthcare systems in order to ensure the representativeness of the sample.

Enrollment will start in each country when sacubitril/valsartan is available for clinical use. Assuming that the penetration of sacubitril/valsartan into clinical practice will be slow immediately after launch, the enrollment of sacubitril/valsartan patients will take a significantly longer time than including SoC patients. At each country level the enrollment of sacubitril/valsartan patients will be continuous, while the enrollment of SoC patients will be divided into two phases, where approximately one half is immediately enrolled at the start of the study and the other half is enrolled during the last part of enrollment into the sacubitril/valsartan group (see Figure 7-1). By structuring the enrollment of SoC patients in this two-wave pattern, the possibility is created to compare the baseline demographic and medical characteristics of patients that drive the choice of physicians toward individualized SoC or sacubitril/valsartan (main objective) and see if their approach changes over time, after the launch of sacubitril/valsartan.

LCZ696 launch in Country A ~ 50 % ~ 50 % SoC SoC 100% LCZ696 Phase 2 Phase 1 Phase 3 12 months В ~ 50 % ~ 50 % LCZ696 launch in Country SoC SoC 100% LCZ696 Phase 1 Phase 2 Phase 3 12 months S ~50 % ~ 50 % LCZ696 launch in Country SoC 100% LCZ696 Phase 1 Phase 2 Phase 3

Figure 7-1 Enrollment schedules (examples) on single country level

Overall enrollment: 24 months

Enrollment schedule for each country will depend on enrollment numbers in SoC and sacubitril/valsartan groups and thus might need to be divided into phases, where SoC enrollment is split up in two phases, while LCZ696 enrollment is continuous (examples A-C). SoC = standard of care, LCZ696 = sacubitril/valsartan

12 months

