7.2.3 Exclusion criteria

- 1. Concomitant or planned participation in any interventional clinical trial
- 2. Patients who are receiving ongoing treatment with sacubitril/valsartan that has been started prior to market launch in their respective country, e.g. within a clinical trial or early access program.
- 3. Patient still within the safety follow up phase of any previous interventional or non-interventional trial using sacubitril/valsartan (LCZ696), independently whether they received sacubitril/valsartan or the comparator.
- 4. Acute decompensated HF requiring hospitalization at the moment of enrollment.
- 5. Existing contraindications according to approved product information

No additional restrictions for inclusion or exclusion are provided in order to ensure that the patients enrolled are as close as possible to (i.e. representative of) the real population of CHF patients with reduced LVEF managed in the office-based setting.

Page 21

7.3 **Variables**

- Demographics (age, gender, living at home or institution, relationship status, education)
- Medical history and comorbidity burden (with focus on duration of HF, etiology of CHF, last hospitalization for HF, cardiovascular conditions, specific comorbidities such as diabetes, renal insufficiency, COPD, anemia, obesity, cancer)
- Clinical Events (both retrospectively over the past 12 months and prospectively, as applicable):
 - Death (CV related and non-CV related, only prospectively)
 - Hospitalizations (defined as at least one overnight staying): number, elective or not, reason for hospitalization (CV related, HF related, non CV related)
 - **Myocardial Infarction**
 - Stroke
- Number of visits (other than hospitalization) by provider and primary reason during follow-up:
 - Emergency room/department
 - Outpatients office visits (general practitioner; cardiologist; internist; other specialist)
 - Cardiology (day) clinic
 - Device clinic
 - Nurse services/ day clinic
 - Rehabilitation facilities
- Diagnostic and therapeutic procedures utilized during follow-up (Results will be collected only as available for blood potassium, blood creatinine, BNP, NT-proBNP and for echocardiographic EF. In all other cases, the eCRF will only capture if the procedure has been performed and its primary reason)
 - Echocardiogram (LVEF in % if available)
 - ECG / stress ECG
 - Chest X ray
 - Pulmonary function tests
 - Computed Tomography of the Heart
 - Cardiac Magnetic Resonance Imaging
 - Cardiac catheterization

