7.5 Study size

The main objectives of the ARIADNE study are to describe:

- 1. The profiles of patients who are prescribed sacubitril/valsartan or SoC in terms of demographics, medical history, HF status, comorbidity burden.
- 2. The profiles of patients who are prescribed sacubitril/valsartan and do not achieve and maintain the target dose of 200 mg BID within the observation period of 12 months in terms of demographics, medical history, HF status, comorbidity burden.

Overall the present NIS will enroll 6000 patients on SoC and 6000 patients on sacubitril/valsartan. Accordingly, 6000 patients will be available in each group for the first main objective.

In the randomized controlled study TITRATION (Senni 2015), 76.2% of patients were able to reach and maintain the target dose of sacubitril/valsartan over 12 weeks, while 23.8% of patients were not. Despite the absence of other data on the titration of sacubitril/valsartan in the literature, in real-life a higher proportion of patients failing up-titration to the target dose can be expected, due to tolerability reasons and lack of patients' or physicians' compliance. Assuming that the actual lack of up-titration could realistically be as high as 50% of all patients, 3000 sacubitril/valsartan patients will be available for the second of the two main objectives.

The two main objectives are focused on description of patient profiles. With respect to the first main objective, a total of 6000 patients in each group will allow to estimate patient profile parameters with the following precision: The two-sided 95% confidence interval (CI) for qualitative parameters (e.g. gender) will be no longer than 2.6% (i.e. estimate \pm 1.3%), and 95% CIs for quantitative parameters (e.g. age) will not exceed 5.0% of the underlying standard deviation (SD) (i.e. estimate \pm 0.025*SD).

The number of SoC patients enrolled in phase 1 and in phase 3 respectively (first objective) and the number of patients on sacubitril/valsartan not achieving the target dose (second objective) are expected to be approximately 3000 each. With a sample size of 3000 patients, the two-sided 95% CI for qualitative parameters (e.g. gender) will be no longer than 3.6% (i.e. estimate \pm 1.8%), and 95% CIs for quantitative parameters will not exceed 7.2% of the underlying standard deviation (SD) (i.e. estimate \pm 0.036*SD).

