7.7 Data analysis

All analyses will be performed by the designated CRO.

Only descriptive data analyses will be carried out, supported by calculation of confidence intervals. No statistical testing will be performed.

The two patient populations will be considered and analyzed separately. The SoC group will allow the representative picture of current CHF management as mentioned above. The Sacubitril/valsartan stratum will provide early insight into the adoption of this new therapy, once it will be available in the different countries. Therefore also strata for patients switching between SoC and Sacubitril valsartan will be analyzed upon adequate subgrouping.

The two studied groups, SoC and sacubitril/valsartan, are expected to differ significantly depending on the progressive adoption of sacubitril/valsartan by the prescribers – this will be assessed by stratified analysis according to the above described enrollment phases. In addition, besides baseline characteristics of the patients leading to the physicians' decision to prescribe sacubitril/valsartan or continue SoC, no inferences can be made from the comparison of the characteristics of both populations. For the same reason, no comparison of data obtained during the follow-up phase between the treatment groups is planned. Similarly, no safety comparisons will be performed between SoC (where in most cases an established therapy is merely continued) and sacubitril/valsartan (where a new therapy is prescribed).

Analyses will be performed for the total sample and stratified by demographic, anamnestic and medical factors (e.g. sex, duration of HF, severity of HF, previous HF-treatment) using an adequate grouping. Similarly, data will be also analyzed stratified according to enrollment phase (phase 1 and phase 3) and treatment group (e.g. SoC, valsartan/sacubitril, switching between both groups).

The Statistical Analysis Plan will be created as a separate document prior to data base lock for any analysis (e.g. interim analyses, final analysis). This document will contain sufficient details to enable the generation of the analysis of the NIS and specifies:

- the statistical database underlying the evaluation, including all adjustments, implementations and the calculation of derived variables,
- the detailed establishment of the analyzed population(s), and
- the statistical procedures.

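### Unweighted total-sample figures cannot describe the overall European outpatient HFrEF population, because the 50:50 treatment mix is set by the design

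*Protocol*

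**What the plan says.** **Target.** Section 6 sets additional objectives about a whole population: "To describe the overall HFrEF population managed in the outpatient sector in Europe in terms of demographics", and "To describe HF-treatment (pharmacological and non-pharmacological) in the outpatient sector in Europe and in individual countries/country clusters". It also asks for rates of major HF outcomes and for healthcare resource use in European routine practice.

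**Sample.** Section 7.2.1: "The study will include overall 6000 patients on SoC and 6000 patients on sacubitril/valsartan". Section 7.5 repeats the same numbers. Sections 7.2.1 and 7.9 explain how the mix arises: sacubitril/valsartan enrolment runs without interruption, while SoC enrolment is split into two waves and stops during phase 2.

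**Expectations.** Section 7.2.1 gives the reason for this schedule: "Assuming that the penetration of sacubitril/valsartan into clinical practice will be slow immediately after launch". Section 7.7 expects the two groups to differ.

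**Analysis.** Section 7.7 says the two groups are analysed separately, and then: "Analyses will be performed for the total sample and stratified by demographic, anamnestic and medical factors". It states no weighting. It also says: "The SoC group will allow the representative picture of current CHF management".

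**Eligibility.** Exclusion 5 in Section 7.2.3 reads "Existing contraindications according to approved product information". It names neither a product nor a group. The sentence after the list says that no further restrictions apply, so that enrolled patients stay representative of the real population.

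**The concern.** The share of sacubitril/valsartan patients in the total sample is a design constant of 50%. It is not an observation about European practice. If real uptake is well below one half, as the protocol's own premise of slow penetration suggests, every total-sample figure gives sacubitril/valsartan patients too much weight. On any characteristic where the groups differ, the pooled value is pulled towards the sacubitril/valsartan group, and the large sample puts a narrow interval around that shifted value.

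At stake are the additional objectives that speak of the overall population, treatment in Europe, outcome rates and resource use. Section 7.9 does discuss the two-wave SoC enrolment, but only as a possible incentive to prescribe, not as something that changes the composition of the pooled sample.

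**Working it through.** **Inputs from the protocol.** 6000 patients per group (Sections 7.2.1 and 7.5), hence 12000 in total with a sacubitril/valsartan share of 0.5. Stated precision is in Section 7.5.

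**Inputs that are assumed.** The protocol gives neither the true share π nor the group difference d. I take π = 5%, 10%, 20% and 30%, and d = 5, 10 and 20 percentage points.

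**Step 1: reproduce the stated precision.** The half-width for a proportion at p = 0.5 is 1.96 × √(0.25/n); for a mean it is 1.96 × SD/√n.

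- n = 6000: 1.265 points (length 2.53%; stated 2.6%) and 0.0253 SD (length 5.06% of SD; stated 5.0%, a rounding difference).
- n = 3000: 1.789 points (length 3.58%; stated 3.6%) and 0.0358 SD (length 7.16% of SD; stated 7.2%).

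The stated figures hold. For the pooled sample, n = 12000 gives 0.895 points.

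**Step 2: bias of the unweighted pool.** Let a be the value in SoC patients and b = a + d the value in sacubitril/valsartan patients. The pool estimates 0.5a + 0.5b. The population value is (1 − π)a + πb. The bias is therefore (0.5 − π) × d. In points, with multiples of the 0.895-point half-width in brackets:

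| π | d = 5 | d = 10 | d = 20 |
|---|---|---|---|
| 5% | 2.25 (2.5) | 4.5 (5.0) | 9.0 (10.1) |
| 10% | 2.0 (2.2) | 4.0 (4.5) | 8.0 (8.9) |
| 20% | 1.5 (1.7) | 3.0 (3.4) | 6.0 (6.7) |
| 30% | 1.0 (1.1) | 2.0 (2.2) | 4.0 (4.5) |

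With d = 0 the bias is zero.

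**Step 3: the SoC group as a stand-in for everyone.** Its bias is −π × d. At d = 10 this is −0.5, −1.0, −2.0 and −3.0 points for π = 5%, 10%, 20% and 30%, against the 1.265-point half-width at n = 6000. In absolute size it is smaller than the pooled bias whenever π < 0.5 − π, that is, below a share of 25%.

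**Step 4: price of weighting.** With weights π/0.5 and (1 − π)/0.5, the Kish effective sample size is 12000 divided by the mean squared weight:

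- π = 5%: mean squared weight (0.1² + 1.9²)/2 = 1.81; effective n 6630; half-width 1.20 points.
- π = 10%: (0.2² + 1.8²)/2 = 1.64; effective n 7317; 1.15 points.
- π = 20%: (0.4² + 1.6²)/2 = 1.36; effective n 8824; 1.04 points.

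All three lie within the 1.3 points that Section 7.5 accepts for a single group.

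**The case against.** The best defence is that Section 7.7 already analyses the two groups separately and also stratifies by treatment group and enrolment phase. The two main objectives, as listed in Sections 6 and 7.5, are group descriptions, and the sample size rests on group-level precision alone. This stands, and it confines the point to the additional objectives and the total-sample results.

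A second defence is that weighting is normal SAP content and the SAP is not at hand. That is fair for the method. But the quotas, the pause, the total-sample analysis and the population wording are all protocol text. The protocol describes no count of eligible patients by treatment from which weights could come, and Section 7.9 concedes that consecutive enrolment cannot be verified. A separate enrolment description document is listed in Annex 1 and was not available.

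Three stronger readings are tempting, and the documents do not support them.

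- *A reader might infer that reported European ACEI/ARB use will be grossly wrong*, since the new drug replaces these agents. The treatment endpoint listed in Section 7.1 is a description of SoC treatments by country, which does not depend on the pooled mix, and the protocol gives no figure for ACEI/ARB use.
- *A reader might infer that the SoC group is just as misleading.* At low uptake its error is small: 1.0 point at a 10% share and a 10-point difference, below its own half-width. The sentence can also be read as referring to care without the new drug.
- *A reader might infer that exclusion 5 removes a main driver of treatment choice.* Its scope is ambiguous as written, and nothing in the protocol allows the effect to be sized.

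**Conclusion.** The point holds for the additional objectives on the overall outpatient HFrEF population, HF treatment in Europe, outcome rates and resource use. The unweighted total sample cannot answer them, because its treatment mix comes from the quota and the phase 2 pause. Across assumed shares of 5% to 30% and differences of 5 to 20 points, the bias runs from about 1 to 9 points, or 1.1 to 10.1 times the pooled half-width. Both inputs are assumptions. What the protocol supplies is the direction of the argument: slow uptake and groups that are expected to differ. Where they do not differ, nothing is lost.

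The claim that SoC is representative of current management needs qualifying rather than withdrawing, and the qualification matters more as uptake grows, so more in phase 3 than in phase 1. The scope of exclusion 5 is a separate wording matter and adds no weight to the quota argument.

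**What to change.** 1. In Sections 6 and 7.7, state that population statements rest on the separately reported cohorts, and that unweighted total-sample results describe only the patients enrolled.
2. If an overall figure is wanted, weight the cohorts by country to a stated treatment share, and name its source. Show results over a range of shares. A share taken from phases 1 and 3, when both groups are open, depends on consecutive enrolment that cannot be verified. Section 7.2.1 also admits patients already started on the drug after launch.
3. Reword the SoC sentence in Section 7.7 so that the group represents patients not on sacubitril/valsartan.
4. Separately, reconcile exclusion 5 with the representativeness statement that follows it in Section 7.2.3, by saying which product and which group the exclusion covers.

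Items 1, 3 and 4 are changes of wording. Item 2 costs some precision: a half-width of about 1.0 to 1.2 points for shares of 5% to 20%, instead of 0.9, plus the work of obtaining a defensible share for each country.

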7.1 Study design

This is an observational, European NIS with prospective collection of primary data. Data will be collected for two groups of HFrEF patients: Patients who receive individualized SoC and patients for whom the physician has decided to prescribe sacubitril/valsartan. If the patient is to be started on sacubitril/valsartan, the decision to prescribe sacubitril/valsartan has to be made independently from the participation in this study. This independency is ensured by the fact that patients with any CHF treatment, who satisfy the inclusion and exclusion criteria, can be enrolled. The treating physician can adapt the CHF treatment during the follow-up phase of the study according to his/her decision. The patients will be followed up over 12 months after enrollment, independently whether they remain on the same CHF treatment they received at the time of enrollment, or are switched to another CHF treatment (see Section 7.2). If during the follow-up phase patients are switched from SoC to sacubitril/valsartan or *vice versa*, they will remain nominally allocated to their original group (i.e. based on their treatment at the time point of enrollment). Details on the analysis of different CHF treatment populations will be provided in the statistical analysis plan.

The main objective of the study is to describe the profiles of symptomatic CHF patients who are prescribed sacubitril/valsartan or SoC in terms of demographics, medical history, HF status, comorbidity burden at the time point of the baseline visit.

A co-primary objective is to describe the profiles of symptomatic CHF patients who are prescribed sacubitril/valsartan and do not achieve and maintain the target dose of 200 mg BID within the observation period of 12 months in terms of demographics, medical history, HF status, comorbidity burden.

The **endpoints yielding to the primary objectives** are descriptive in nature and will be derived from the baseline demographic and medical history variables and sacubitril/valsartan treatment data (see Section 7.3).

Additional endpoints:

- Number of patients achieving a target sacubitril/valsartan dose of 200 mg BID
- Number of patients maintaining the target dose of sacubitril/valsartan 200 mg BID
- Description of SoC treatments (drug and non-drug) according to each participating country (e.g. drug, daily dose).
- Incidence of major CV events and adverse events (AE)
- Change in NYHA status
- Incidence of hospitalizations, doctor visits and diagnostic procedures, and reasons therefore
- Description of baseline health-related quality of life and change of QoL scores throughout the observation period (only in those sites where EQ-5D and/or KCCQ QoL questionnaires are part of routine CHF management)
- Description of baseline BNP / NT-proBNP levels and their changes throughout the observation period (only if measurements are available or in those sites where these measurement are part of the routine CHF management)

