The **endpoints yielding to the primary objectives** are descriptive in nature and will be derived from the baseline demographic and medical history variables and sacubitril/valsartan treatment data.

Study design

This is an observational, European NIS with prospective collection of primary data. Data will be collected for two groups of HFrEF patients: Symptomatic patients who receive the current individualized standard of care (SoC) for the treatment of CHF and patients for whom the physician has decided to prescribe sacubitril/valsartan. The decision to prescribe sacubitril/valsartan has to be made independently from the participation in this study. This independency is ensured by the fact that patients with any CHF treatment, who satisfy the inclusion and exclusion criteria, can be enrolled. Switching between different CHF treatments (e.g. between SoC and sacubitril/valsartan) is allowed at any time as per decision of the investigator.

Enrollment will start in each country when sacubitril/valsartan is available for clinical use. Assuming that the penetration of sacubitril/valsartan into clinical practice will be slow immediately after launch, the enrollment of sacubitril/valsartan patients will take a significantly longer time than enrollment of SoC patients. At each country level the enrollment of sacubitril/valsartan patients will be continuous, while the enrollment of SoC patients will be divided into two phases, where approximately one half is immediately enrolled at the start of the study and the other half is enrolled during the last part of enrollment into the sacubitril/valsartan group.

All patients, independent of their treatment are to be enrolled consecutively, in order to avoid selection bias.

Population

ARIADNE will include consecutive adult HFrEF patients who are treated by either office-based cardiologists or selected primary care physicians (recognized as HF specialists) all over Europe.

Inclusion criteria

- 1. Written informed consent provided by the patient or legal representative for participating in the study (according to country specifications)
- 2. Age ≥ 18 years
- 3. Patients with symptomatic CHF (NYHA class II IV) with a documented reduced left ventricular ejection fraction (LVEF) as assessed by clinical examination and any imaging technique performed anytime in the past.

Exclusion criteria

- 1. Concomitant or planned participation in any interventional clinical trial

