7.9 Limitations of the research methods

Potential limitations of the present study are due to its non-interventional character, where no stipulation regarding data collection can be made. In the present study, not all involved sites use QoL questionnaires or certain lab parameters within the routine management of CHF and thus, these data will not be available for all patients. In addition, there is no randomization or blinding within a NIS; especially QoL data from non-blinded patients need to be interpreted carefully. However, the non-interventional character of the study is the only way to obtain real-life data. In order to obtain a representative sample of the population of CHF patients from the outpatient sector, the ARIADNE NIS will not mandate diagnostic nor therapeutic processes which would distort the recruitment.

However, non-cardiac disorders as well as HFpEF (HF with preserved systolic function) can be confused with HFrEF. In order to ensure sufficient homogeneity of the patient population, inclusion will require that the patient has documentation of reduced left ventricular systolic function (LVEF) in the past through any imaging technique.

To reduce the selection bias in the patients an investigator will include into the NIS, the physician is urged to offer enrollment to all consecutive patients and not select patients from his patient database. However compliance with this requirement cannot be verified due to data privacy regulations; therefore the investigators are asked to diligently follow the good epidemiological practice requirement of offering participation to this study to consecutive patients.

A potential selection bias might arise from the bi-phasic enrollment of SoC patients. This risk is mitigated by following design features:

- there is no minimal time requirement for the patient being on SoC prior to enrollment into the study and
- patients can be switched to the optimal therapy as per judgement of the investigator at any time of the study.

Thus, there is no incentive for increased prescribing (and therefore for a selection bias) sacubitril/valsartan during phase 2 of enrollment (when enrollment into the SoC group is paused). If a patient is receiving SoC during enrollment phase 2 and still would like to participate in the NIS when enrollment into this group is commenced again (i.e. phase 3) he/she can be enrolled into the SoC group at that time, as there are no temporal stipulations regarding duration of SoC treatment.

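### Independence of the prescribing decision is said to be ensured by any-treatment enrolment, but that does not hold in phase 2, when only sacubitril/valsartan patients can enter

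*Protocol*

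**What the plan says.** Section 7.1 (and section 2, Study design) requires the prescribing decision to be made independently of study participation and adds: "This independency is ensured by the fact that patients with any CHF treatment, who satisfy the inclusion and exclusion criteria, can be enrolled".

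Section 7.2.1 then sets the enrolment pattern. For the drug, "At each country level the enrollment of sacubitril/valsartan patients will be continuous". For the other cohort, "the enrollment of SoC patients will be divided into two phases, where approximately one half is immediately enrolled at the start of the study". SoC entry reopens for the remainder only towards the end of sacubitril/valsartan enrolment. The note to Figure 7-1 makes phasing conditional: a country's schedule may need to be split, depending on its numbers. A further note in 7.2.1 requires the treatment decision to rest on clinical judgement and to come before enrolment. The same section admits patients who started sacubitril/valsartan earlier, provided this was after commercial launch.

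Section 7.9 speaks of the period "during phase 2 of enrollment (when enrollment into the SoC group is paused". It names a potential selection bias from the two-wave SoC scheme and offers mitigations: no minimum period on SoC, freedom to switch at any time, and entry in phase 3 for an SoC patient seen in phase 2. It concludes: "Thus, there is no incentive for increased prescribing (and therefore for a selection bias) sacubitril/valsartan during phase 2 of enrollment".

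On consecutive enrolment, section 2 says: "All patients, independent of their treatment are to be enrolled consecutively, in order to avoid selection bias". Section 7.9 concedes that compliance with this cannot be verified.

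**The concern.** The safeguard is a statement of fact: a patient can be enrolled whatever the treatment, so a physician has no study-related reason to prefer one. If enrolment is open to one treatment only, that reasoning fails, and it fails in exactly the period when entry depends on the choice being studied.

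At stake is the first main objective. Section 7.2.1 ties it to the baseline characteristics that lead physicians to SoC or to sacubitril/valsartan, and to whether their approach changes after launch. Section 7.7 rules out inference from comparing the two groups except on those baseline characteristics, and plans no between-group comparison of follow-up data. The one contrast the plan keeps is therefore the one that relies on prescribing being uninfluenced by access to the study.

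**Working it through.** The main check is of logic: the enrolment rules set side by side, by phase.

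| Phase | Sacubitril/valsartan entry (7.2.1) | SoC entry (7.2.1, 7.9) | Can a patient on any treatment enter (7.1)? |
|---|---|---|---|
| 1 | open | open | yes |
| 2 | open | paused | no |
| 3 | open | open | yes |

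The premise in 7.1 is true in phases 1 and 3 and false in phase 2.

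Next, does anything else in the protocol restore it in phase 2?

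1. *No minimum period on SoC (7.9).* This eases entry when the SoC group is open. It has no effect while the group is closed.
2. *Free switching (7.9).* This protects the patient's care. It does not let an SoC patient enter in phase 2. Under 7.1 a patient who switches back stays counted in the group of entry.
3. *Deferred entry in phase 3 (7.9).* This weakens the incentive, because the SoC patient is not lost for good. A difference remains between entering now and waiting, and the deferred patient must still be eligible, on SoC and willing when phase 3 opens.
4. *Decision before enrolment (7.2.1).* This fixes the order of events in every phase. It does not show that a decision was made without knowing which group was open.
5. *Consecutive enrolment (2, 7.2.1, 7.9).* In phase 2, SoC patients are not enrolled as they present, so the rule cannot apply irrespective of treatment. It also cannot be verified, so it does not work as a back-up.

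Items 1 to 4 reduce the incentive to differing degrees. None supports the conclusion that there is no incentive.

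*Size.* The text gives neither the length of phase 2 nor the number enrolled in it. As a range only, assume that every country has a phase 2, that sacubitril/valsartan accrual is uniform, and that phase 2 takes a fraction f of the enrolment window. The number enrolled in phase 2 is then f × 6000. Precision uses the formula that reproduces section 7.5, half-width = 1.96 × √(0.25/n):

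- n = 6000: 1.96 × √(0.25/6000) = 1.27% (stated ±1.3%)
- n = 3000: 1.96 × √(0.25/3000) = 1.79% (stated ±1.8%)

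| f | Enrolled in phase 2 | Half-width | Enrolled in phases 1 and 3 | Half-width |
|---|---|---|---|---|
| 0.25 | 1500 | 2.53% | 4500 | 1.46% |
| 0.50 | 3000 | 1.79% | 3000 | 1.79% |
| 0.75 | 4500 | 1.46% | 1500 | 2.53% |

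These counts are ceilings on the patients enrolled without the stated safeguard. They do not count altered decisions. Patients started before phase 2 opened, and countries without a phase 2, must be taken out. The protocol also expects slow uptake just after launch, so uniform accrual is a convenience. The table does show that describing phase 2 separately remains precise across the range.

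*Analysis.* Section 7.7 first refers in general to stratifying by the enrolment phases, but where it lists the strata it names only phases 1 and 3. Sacubitril/valsartan patients from phase 2, where any distortion would appear, have no named stratum.

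**The case against.** The strongest reply is that the protocol does not hide the issue. Section 7.9 names the selection bias under limitations and argues against it, and 7.2.1 adds a separate instruction on the order of decision and enrolment. The drug must be on the market before a country starts, so nobody needs the study to obtain it, and the data come essentially from routine care. The study is descriptive with no testing. The sentence on consecutive enrolment directly follows the description of the two-wave scheme and can be read as applying within whichever group is open.

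Much of this stands, and it limits the point. A reader might infer any of the following, none of which the documents support:

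- *That prescribing in phase 2 was in fact driven by the study.* No passage describes a benefit from entering then rather than in phase 3. Pressure on sites to recruit is plausible but is not shown.
- *That every sacubitril/valsartan patient enrolled in phase 2 is affected.* Section 7.2.1 admits patients started earlier, whose prescription the pause cannot have influenced, and phasing may not apply in every country.
- *That patients would be started, enrolled and switched back.* This is speculative and would leave a trace: reasons for switching and discontinuation are recorded, and switchers are analysed as strata.
- *That SoC enrolment must be kept open at a low rate in phase 2.* SoC patients are expected to enrol faster than sacubitril/valsartan patients. A small quota would fill early and recreate the pause, or would need rationing, which itself breaks consecutive enrolment.

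What the reply does not reach is the wording. Disclosing a risk and then declaring it absent on grounds that do not remove it still misinforms the reader. An instruction on sequence is not the property that 7.1 says ensures independence.

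**Conclusion.** The point holds as a false assurance. Where a phase 2 occurs, the property that sections 2 and 7.1 rely on is absent, and the no-incentive conclusion in 7.9 does not follow from its reasons. The consecutive-enrolment statement in section 2 needs the same qualification.

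The size is unknown. It is bounded by the sacubitril/valsartan patients who were both started and enrolled during a phase 2; the 1500 to 4500 range is an illustration of enrolment under stated assumptions and includes patients who are not affected. Whether any decision was influenced cannot be told from the documents. The stand-alone enrolment description document listed in Annex 1 may set out the phases in more detail, but it is not available here and would not make the text of 7.1 true for phase 2.

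The correction is worth making because it is cheap and bears on the one between-group contrast that the plan retains.

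**What to change.** - **Sections 2 and 7.1:** limit the statement that independence is ensured to phases 1 and 3.
- **Section 7.9:** replace the no-incentive conclusion with a statement that in phase 2 independence is not protected by design and rests on the instruction in 7.2.1; keep the mitigations as factors that reduce the risk.
- **Sections 2, 7.2.1 and 7.9:** say that consecutive enrolment applies within the groups open at the time.
- **Section 7.3:** record the date of the prescribing decision, or of treatment start, relative to the date of the study invitation. This separates patients started before phase 2 from those started during it.
- **Section 7.7:** add phase 2 to the named phase strata. Describe sacubitril/valsartan patients started and enrolled in phase 2 next to those from phases 1 and 3, and show the main profile also without them.

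Cost: text changes, one date item in the eCRF and one further stratum in the tables. No extra patients and no change to the two-wave scheme or to the precision stated in 7.5. The profile shown without these patients is less precise than the full one, as in the range above, but it stands alongside the main profile and does not replace it.
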